9.5 Exploratory Analysis

Analysis of other factors influencing adherence to at home anticoagulation in this population are considered exploratory. To explore what factors other than type of anticoagulant may be impacting adherence, we plan to perform a logistic regression with the outcome variable of PDC. Covariates will include the following: age, gender, ethnicity, marital status, living situation, occupational status, education level, annual household income, insurance status, history of prior blood clot, number of daily medications, discharge destination, study arm, and items from the Satisfaction Questionnaire. Univariate regression will be performed first followed by multivariate regression including all variables that were significantly associated on univariate regression.

A second exploratory analysis will be comparing elements of the novel satisfaction questionnaire trial between the apixaban and enoxaparin arms. Items from this questionnaire may be compared by presenting descriptive statistics without formal tests for statistical significance in order to explore how patient satisfaction varies between the study arms and allow future physicians to give anticipatory guidance.

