- National Institute of Health (NIH) Patient-Reported Outcomes
 Measurement Information System (PROMIS) Medication
 Adherence Scale (PMAS) a validated, nine-item, patient-reported
 measure of medication adherence¹
- 2. Patient Satisfaction a series of independent questions that investigate barriers to adherence specific to apixaban or enoxaparin

To address our secondary objective of comparing cost, secondary endpoints also include:

- 3. Patient out of pocket cost for anticoagulant prescription (in dollars)
- 4. COST-FACIT, a 12-item survey developed and validated in the cancer population for assessing patient-reported financial distress due to healthcare costs²

Study Population:

Inclusion Criteria: All patients undergoing RC with urinary diversion and pelvic lymph node dissection for urothelial bladder cancer (any T stage, N0-1, M0) at the participating institutions.

Exclusion Criteria:

- 1. Preoperative use of a therapeutic dose of anticoagulant (this notably does *not* exclude patients taking antiplatelet agents)
- 2. Failure to undergo radical cystectomy with concurrent urinary diversion and pelvic lymph node dissection
- 3. Failure to be discharged by POD14
- 4. Failure to be discharged on prophylactic enoxaparin or apixaban.
- 5. Any medical condition which precludes treatment with *either* enoxaparin *or* apixaban (including dialysis,hemophilia, or any other bleeding diathesis)
- 6. Inability to communicate over the phone in English

Due to the natural history of bladder cancer, the expected population will be mixed in age, race, gender, and general health status, though likely to be majority white males between the ages of 50-80 in generally good health status (enough that they are safe to undergo RC, which is a major surgery).

Target sample size is 108 participants

Enrolling Sites: Hospital of the University of Pennsylvania (HUP), Philadelphia, PA

Vanderbilt University Medical Center, Nashville, TN

Description of Study Intervention:

Enoxaparin and apixaban are both established treatments in clinical practice and considered acceptable standards of care. However, enoxaparin has historically been utilized for extended prophylaxis prior to the availability of apixaban and is slightly more commonly prescribed. Hence, in this study, randomization to apixaban will be considered the intervention for convention.

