9 STATISTICAL CONSIDERATIONS

9.1 General Approach

Continuous variables will be presented as means with standard deviation or median with interquartile range. All statistical tests of significance will be two-sided with alpha level 0.05. Stata will be used for all statistical analysis.

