9.7 Populations for Analyses

The analysis of primary endpoint, PDC, as well as analyses comparing the results of the questionnaires will be conducted using an Intention-to-Treat (ITT) Dataset consisting of all randomized participants. We expect minimal crossover after randomization however if there is significant crossover we would also perform the analysis in an "As Treated" (AT) dataset consisting of participants categorized to the drug they ultimately received after crossover. Cost analyses will be performed using a dataset of all prescriptions (there may be more than one prescription per participant if there is crossover between study arms, though again this is expected to be minimal). Safety analyses will be performed in the ITT dataset as well as in participants who meet criteria for "adherent" to their anticoagulant (as defined above in section 9.4). Missing data will be assumed random and discarded from all analyses; missing data is expected to be low as there are only two study visits.

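### The exploratory adherence regression lets study arm and POD30 satisfaction items compete for one model by univariate screening, so its multivariable coefficients cannot be read as the drug effect or as independent determinants of adherence

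*Combined protocol and SAP*

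**What the plan says.** Section 9.5 states its aim as "To explore what factors other than type of anticoagulant may be impacting adherence" and its method as "we plan to perform a logistic regression with the outcome variable of PDC". It names 12 patient-level covariates, from age to discharge destination, then adds "study arm, and items from the Satisfaction Questionnaire". The model is built in two steps: "Univariate regression will be performed first followed by multivariate regression including all variables that were significantly associated on univariate regression". No variable is forced in, and arm is treated like any other candidate. No separate screening level is given, so the general rule in 9.1 applies: "All statistical tests of significance will be two-sided with alpha level 0.05".

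The Synopsis describes the satisfaction questions as "a series of independent questions that investigate barriers to adherence specific to apixaban or enoxaparin". Section 7.1 presents them as possible reasons for compliance or noncompliance with the two drugs. The schema (1.2) and section 4 place them at the POD30 contact, where section 9.3 also has the remaining pills or vials counted. Section 7 lets participants answer the questionnaires through an emailed link, while the count must be done by phone.

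On incomplete data, 9.7 says: "Missing data will be assumed random and discarded from all analyses".

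**The concern.** The items are measured after randomisation, at the end of the period over which adherence is counted. Two causal readings are open, and the model cannot tell them apart.

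- **Pathway.** Objective 3 in the Synopsis expects enoxaparin barriers to show up as operational difficulty and dissatisfaction, and apixaban barriers to come from coverage and cost. That runs from drug, through the patient's experience of it, to adherence. Adjusting arm for such an item removes part of the effect of drug.
- **Reverse causation.** A participant who stopped early may rate the drug differently because of stopping. For those who use the emailed link, the answers can come after the count.

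The screen creates a second difficulty whichever way it falls. If arm passes, it is adjusted for its own consequences. If arm fails, drug-linked items can enter without it and act as proxies for the drug, which defeats the aim of finding factors other than the drug. The p-values and intervals of the final model also ignore the selection that produced it. The risk is that consequences of non-adherence, or differences between the drugs, are reported as patient-level determinants of adherence.

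**Working it through.** The plan gives no figure for this regression, so there is nothing to reproduce. The calculations below show the size of each effect under stated assumptions.

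**Inputs from the plan.** Analysis group 90 (5.3), 45 per arm (9.3.1), 1:1 allocation (4.1); 12 named covariates plus arm = 13 candidates (9.5); level 0.05 (9.1). The number of satisfaction items is not given; I take 5 or 10.

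**1. False selections when no candidate matters.**

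Expected number = k × 0.05. Chance of at least one = 1 − 0.95^k if the tests are independent.

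- k = 13: 0.65 expected; 1 − 0.95^13 = 0.487
- k = 18 (5 items): 0.90 expected; 1 − 0.95^18 = 0.603
- k = 23 (10 items): 1.15 expected; 1 − 0.95^23 = 0.693

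A simulation with n = 90 and 2,000 runs gave 49%, 60% and 69%. Of the noise variables selected, 88%, 85% and 82% respectively were still below 0.05 in the multivariable model, so the second step removes few of them. Estimates are also inflated: a true standardised effect of 0.20 averaged 0.29 in the 46% of runs in which it was selected.

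**2. The arm coefficient when an item is in the model.**

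Let A be arm, S one item, Y PDC and U an unmeasured shared cause. The effect sizes are assumptions, and a linear model is used for simplicity. Noise in S has SD 1.

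- (a) Full mediation: S = A + noise, Y = 0.06·S + noise. Total effect 1 × 0.06 = 0.06; adjusted effect 0.
- (b) Mediation plus shared cause: S = A + 0.8·U + noise, Y = 0.05·S + 0.06·U + noise. Total effect 0.05. Within arm, the slope of U on S is 0.8/(0.8² + 1) = 0.488, so the adjusted effect is −0.488 × 0.06 = −0.03.
- (c) No drug effect: S as in (b), Y = 0.10·U + noise. Total effect 0; adjusted effect −0.488 × 0.10 = −0.05.
- (d) Reverse causation: Y = 0.06·A + noise (SD 0.14), S = A + 0.8·Y/0.14 + noise. Total effect 0.06. The within-arm slope of Y on S is 0.14 × 0.488 = 0.068, and the arm difference in S is 1 + 0.8 × 0.06/0.14 = 1.34. The adjusted effect is 0.06 − 0.068 × 1.34 = −0.03.

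Simulation (n = 90, 2,000 runs each):

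| Scenario | True total | Adjusted, all runs | 95% CI covers total | Arm passes screen | Adjusted, runs where both pass |
|---|---|---|---|---|---|
| (a) | 0.06 | 0.00 | 46% | 57% | 0.016 |
| (b) | 0.05 | −0.03 | 23% | 28% | −0.004 |
| (c) | 0 | −0.05 | 63% | 6% | −0.052 |
| (d) | 0.06 | −0.03 | 7% | 53% | −0.017 |

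The last column is the one that applies under the plan's screen.

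**3. When arm fails the screen.** In the three scenarios with a real drug effect, arm passed in 28% to 57% of runs. It was therefore left out in 43% to 72% (100 − 57 and 100 − 28), although it mattered. In those runs, any drug-linked item that enters is not adjusted for drug.

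**The case against.** The strongest reply is that little depends on this model. Section 9.5 calls it exploratory. The effect of drug on PDC is tested without these covariates in 9.3, and on binary adherence in 9.4. Relating reasons to adherence is what the items were written for. All of this stands and limits the point to a minor one.

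A reader might go further than the documents allow in five ways.

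- **That arm and items always share a model.** They do so only if both pass the screen.
- **That the items come after the outcome.** They follow the outcome window but belong to the same POD30 contact as the count. Only answers given later through the link clearly follow it.
- **That the whole regression is uninterpretable.** The univariate estimates are untouched, and associations with baseline variables can still suggest hypotheses.
- **That this is the analysis for Objective 3.** PMAS, COST-FACIT and the descriptive satisfaction comparison serve it too (sections 3, 9.4 and 9.5).
- **That one arm will be deleted.** The questionnaire is not in the documents. Wording about the two drugs need not mean items asked in one arm only, and 9.5 plans to compare questionnaire items between arms. This is a question for the authors: if any item is asked in one arm only, the rule in 9.7 would drop the other arm, about 45 of 90, from a model using it.

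The 49% and 69% figures also assume that nothing matters and that each candidate is one independent test. Income, education, occupation and insurance are probably correlated, which would lower the chance of at least one false selection. The expected number, 0.65 or 1.15, does not depend on independence. Leaving arm out of the count gives 1 − 0.95^12 = 46%.

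**Conclusion.** The point holds as a low-priority improvement. Followed as written, 9.5 can yield an adjusted arm coefficient that is not the total effect of drug, item coefficients that may reflect reverse causation or stand in for arm, and post-selection p-values and intervals that are too favourable. The multivariable coefficients should not be read as the effect of arm or as independent determinants of adherence.

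The selection figures (about 49%, or 69% with 10 assumed items) rest on a global null and independent tests. The shifts in the arm coefficient rest on assumed effects and a linear model; they show direction and possible scale and are not a forecast.

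A reader might infer that the trial's randomised adherence result is at risk. It is not: the comparisons in 9.3 and 9.4 do not use this model.

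**What to change.** In 9.5:

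1. Replace the univariate screen with one pre-specified model. Force study arm in, and add a short list of baseline covariates chosen in advance by the investigators. Report estimates with confidence intervals and label them hypothesis-generating.
2. Take the satisfaction items out of that model. Report their association with PDC descriptively within each arm, next to the questionnaire comparison that 9.5 already plans.
3. State whether any item is asked in one arm only.

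The revised text should also say how PDC, a proportion, enters a logistic model, since 9.5 gives neither a cut-point nor a fractional form.

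The change needs wording only: no new data, participants or visits. The downside is that the adjusted model considers fewer candidate predictors.

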9.6 Analysis of Safety Endpoints

Given the well-established safety profile of both drugs and their use as SOC after cystectomy there is no formal safety endpoint for this study. However, both bleeding and VTE events will be solicited and tracked (see section 7) for safety analysis. DVT, PE, and a composite

outcome of the two will be compared between the two study arms using a test of proportions. For bleeding events, medical review of the chart by an investigator will determine if the event is Major, Clinically Relevant Non-Major (CRNM), or Minor (see section 7) and these three outcomes will be compared between the two groups as well as a composite outcome of Non-Minor Bleeding (Major and CRNM) using test of proportions.

These as well as any other adverse events will be graded (see section 7) and presented in a descriptive way with any further detail deemed clinically relevant by the PI (including but not limited to the treatment and outcome of the AE) included.

9.7 Populations for Analyses

The analysis of primary endpoint, PDC, as well as analyses comparing the results of the questionnaires will be conducted using an Intention-to-Treat (ITT) Dataset consisting of all randomized participants. We expect minimal crossover after randomization however if there is significant crossover we would also perform the analysis in an "As Treated" (AT) dataset consisting of participants categorized to the drug they ultimately received after crossover. Cost analyses will be performed using a dataset of all prescriptions (there may be more than one prescription per participant if there is crossover between study arms, though again this is expected to be minimal). Safety analyses will be performed in the ITT dataset as well as in participants who meet criteria for "adherent" to their anticoagulant (as defined above in section 9.4). Missing data will be assumed random and discarded from all analyses; missing data is expected to be low as there are only two study visits.

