2.3 Preliminary Institutional Results

Given the earlier data suggesting barriers to adoption include cost, we sought to assess the state of prescription costs at our institution and determine how likely this is to pose a barrier to patient adherence. We reviewed our institution's outpatient pharmacy data from July to December of 2022, including the copays that patients being discharged on prophylactic dose apixaban and enoxaparin face at our institution as well as difficulties encountered with prior authorizations. Data suggest that copays may vary from as low as \$0 to >\$100, and that copays are much more likely to be increased with apixaban (Table 1). Review of prior authorizations show that a substantial number of prior authorizations were submitted, and in particular that denial of these prior authorizations and insurance coverage may pose a problem for both medications, in particular apixaban (Table 2).

Table 1. Patient copays for Enoxaparin and Apixaban

Lovenox PX (30mg & 40mg QD	
Copay (\$)	Count
0	103
0-20	108
21-50	27
51-100	14
>100	17
Total	269

Apixaban PX (2.5mg BID)		
Copay (\$)	Count	
0	15	
0-20	14	
21-50	11	
51-100	3	
>100	4	
Total	47	

Table 2. Outcomes of prior authorizations submitted for Enoxaparin and Apixaban

Prior Authorizations					
Medication	Approved	Denied	Total		
Apixaban	32	9	41		
Lovenox	19	2	21		

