4.1 Minimizing Bias

Patients will be randomized to a prescription for one of the two anticoagulants at the time of postoperative discharge, and instructed to continue the medication until POD30. Randomization will be performed in a simple 1:1 fashion.

The randomization will be non-blinded. Given that this trial aims to explore the real experience of patients on these medications, blinding and placebo would actually detract from the important clinical context and understanding that participants have. Furthermore, enoxaparin and apixaban have different routes of administration (enoxaparin is injectable and apixaban is oral) which makes blinding and placebo infeasible. Blinding of the investigators is not necessary given the outcomes are patient reported surveys and pill/vial counts. Bias will be sufficiently reduced by randomization.

The University of Pennsylvania will serve as the primary site, and Vanderbilt University Medical Center as a second site. The addition of a second site will also introduce variety into the study population and strengthen its applicability.

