9.3.1 Sample Size Calculation

Prior studies suggest the at-home adherence to daily lovenox regimen is around 85%. ^{21,28,34,35} Assuming a baseline PDC in the control group of 85% and non-inferiority margin of 15%, a sample size of 45 subjects per arm, 90 subjects total, will provide 80% power to detect non-inferiority at a one-sided significance level of 0.05. ³⁶

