9.4 Analysis of Secondary Endpoints

The following secondary endpoints will be assessed to further characterize adherence and also related elements of satisfaction and cost, though analyses of these related elements are not dependent on findings of the primary endpoint.

- 1. A binary measure of adherence: adherent vs non-adherent. Adherent is defined as taking *all* intended anticoagulant. Adherence in this definition will be compared using a test of proportions (proportion of patients in one study arm that were "adherent" vs proportion of patients in the other arm that were "adherent") within the ITT and population.
- 2. Cost of the medication. There are several measures of cost that will be studied as endpoints, including overall medication cost, cost paid by insurance, and most importantly participant out of pocket cost. Cost will be measured in dollars and reported as median and as mean depending on the presence of outliers. This will be collected from pharmacy review of prescriptions. Cost will be compared using a rank sum test.
- 3. Scores on the two validated questionnaires given: PROMIS and COST. These validated questionnaires both have scoring systems and a t test of the average score of participants in each arm will be compared (ie average score on COST for participants in apixaban arm vs average score on COST for participants in enoxaparin arm). A rank sum test will be used if distributions have outliers.

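### The cost comparison uses prescriptions as its unit, so a participant who crosses over can count more than once and the analysis does not match the per-patient cost hypothesis

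*Combined protocol and SAP*

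**What the plan says.** Section 9.7 puts the primary endpoint and the questionnaires in a participant-level dataset: these analyses "will be conducted using an Intention-to-Treat (ITT) Dataset consisting of all randomized participants". Cost is treated differently: "Cost analyses will be performed using a dataset of all prescriptions (there may be more than one prescription per participant". The sentence goes on to say when this happens: "if there is crossover between study arms, though again this is expected to be minimal".

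Section 9.4 gives the test: "Cost will be compared using a rank sum test". It states no adjustment for participants who appear more than once, and neither section says whether prescriptions are grouped by the drug prescribed or by the randomised arm.

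The cost question itself is worded in two ways. Objective 2 in the synopsis (section 1.1) predicts a higher median patient out-of-pocket cost in the apixaban group. The table in section 3 speaks of comparing the cost of the two drugs, with the out-of-pocket cost of the prescription as endpoint, and section 7.2 tracks cost separately for each anticoagulant. Section 8.3 promises intention-to-treat and per-protocol analyses after crossover but does not mention cost.

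**The concern.** Participants are randomised, and the hypothesis is about what patients in each group pay. A prescription-level dataset splits a switched participant's spending into separate records, so that person's total is never formed.

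The rank sum test treats every record as an independent observation, and two prescriptions for one person are not. Grouped by drug, the two records fall on opposite sides and, for those records, the comparison is no longer between the groups as randomised. Grouped by arm, the randomised groups are kept but the person is counted twice on one side.

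At stake are the error rate of the test and, more importantly, what the estimated difference means. Section 9.4 singles out participant out-of-pocket cost as the most important of the cost measures.

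**Working it through.** **No figure to reproduce.** The documents give no sample size, power or effect size for cost, so the check asks how much the choice of unit could matter.

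**Inputs from the documents**
- Analysed size: "a sample size of 45 subjects per arm, 90 subjects total" (section 9.3.1).
- Allocation: "Randomization will be performed in a simple 1:1 fashion" (section 4.1).
- Test level: "All statistical tests of significance will be two-sided with alpha level 0.05" (section 9.1).
- Copay counts in the bands 0, 0-20, 21-50, 51-100 and >100 dollars (section 2.3, Table 1): enoxaparin 103, 108, 27, 14, 17 (total 269); apixaban 15, 14, 11, 3, 4 (total 47).

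**Assumptions, not in the documents**
- Crossover of 0-22% per arm, each switch adding one paid prescription.
- Correlation of 0.5 or 0.9 between one person's two copays.
- Band values of 0, 10, 35, 75 and 150 dollars.

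**Step 1: number of records.** Records = 90 × (1 + crossover rate), shown in the table below.

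**Step 2: type I error.** The two-sided rank sum test was simulated with 45 per arm, equal cost distributions for the two drugs and 4,000 replicates. The Monte Carlo standard error is √(0.05 × 0.95 / 4000) ≈ 0.0035. Each range spans the two correlations.

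| Crossover in both arms | Records | Prescriptions by drug | Prescriptions by arm | One total per participant |
|---|---|---|---|---|
| 2% | 91.8 | 0.042-0.054 | 0.052-0.056 | 0.042-0.046 |
| 5% | 94.5 | 0.038-0.045 | 0.051-0.057 | 0.044-0.045 |
| 10% | 99 | 0.035-0.036 | 0.057-0.068 | 0.041-0.045 |
| 20% | 108 | 0.027-0.033 | 0.064-0.078 | 0.046-0.047 |

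Grouping by drug makes the test conservative; grouping by arm makes it anti-conservative. At 2-5% crossover both are close to simulation noise.

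**Step 3: what is estimated.** Means are used only to show the size of the shift.
- Enoxaparin mean copay: (108×10 + 27×35 + 14×75 + 17×150)/269 = 5625/269 = 20.91 dollars.
- Apixaban mean copay: (14×10 + 11×35 + 3×75 + 4×150)/47 = 1350/47 = 28.72 dollars.
- Difference per prescription by drug: 28.72 − 20.91 = 7.81 dollars, whatever the crossover rate.

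The difference per participant, by randomised arm, depends on who switches:
- 10% out of enoxaparin only: 28.72 − (20.91 + 0.10×28.72) = 28.72 − 23.78 = 4.94 dollars (simulated 4.8-5.0, against 7.7-7.8 per prescription by drug).
- 22% out of apixaban and 9.5% out of enoxaparin: (28.72 + 0.22×20.91) − (20.91 + 0.095×28.72) = 33.32 − 23.64 = 9.68 dollars (simulated 9.6-9.8, against about 7.9).

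The shift is therefore about −2.9 dollars in the first case and +1.9 in the second.

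**Step 4: if only the replacement is paid for.** Section 8.3 places crossover before discharge, so the first prescription may never be filled. With 10% out of enoxaparin, the per-participant difference is then 28.72 − (0.90×20.91 + 0.10×28.72) = 28.72 − 21.69 = 7.03 dollars, a shift of only 0.78.

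**The case against.** The strongest reply is that the plan ties a second prescription to crossover alone and expects little of it. Section 8.3 anticipates a single contraindication, low creatinine clearance for enoxaparin, which has no stated link to cost. This stands, and it keeps the point small.

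A second reply is that a per-prescription comparison of drug prices fits the wording of sections 3 and 7.2. That is fair: the documents are ambiguous about the target. But the only stated cost hypothesis is per patient and by group, and even a drug-price comparison would need a test that allows for the same person appearing twice.

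Three stronger readings are tempting, and the documents do not support them.
- A reader might infer that switched participants are mainly those with coverage or cost trouble, because section 2.3 warns that "denial of these prior authorizations and insurance coverage may pose a problem for both medications, in particular apixaban". Its figures, 9/41 (22.0%) denied for apixaban and 2/21 (9.5%) for enoxaparin, are shares of authorisations submitted. They are not shares of participants, and nothing says that a denial leads to a second prescription. Coverage-driven switching could enter only through the case-by-case review in section 8.3. The upper scenario above uses the same percentages purely as assumed crossover rates.
- A reader might infer that split or replacement fills of the same drug are also double counted. Section 9.7 names only crossover as a source of extra records.
- A reader might say that the randomised comparison is lost outright. That holds only for crossover records, and only if grouping is by drug, which is the natural reading but is not written.

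**Conclusion.** The concern holds as a minor flaw in a secondary endpoint. The stated unit breaks independence under either grouping whenever one participant contributes two cost records, and no other section restores a per-participant cost comparison by arm.

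At an assumed 2-5% crossover, the effect on the error rate is negligible. At an assumed 10-22%, the mean difference can move by about 2 to 3 dollars, down or up depending on which arm loses participants, so the choice cannot be defended as conservative. These sizes rest on assumed crossover rates and correlations, on midpoint-type values for the copay bands, and on both prescriptions being paid for. The shift is smaller if only the replacement is filled. The documents give no switching rate, and the prior-authorisation denials do not supply one.

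**What to change.** In section 9.7, define the main cost analysis as one value per participant: the total out-of-pocket cost of all study anticoagulant prescriptions recorded in the pharmacy data through POD30, compared by randomised arm (intention to treat) with the rank sum test already planned. Keep the per-prescription summary by drug as descriptive.

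The cost is about one sentence of text and a sum within participant, using pharmacy records that section 7.2 already plans to review. The drawback is that a participant who fills nothing has a recorded cost of zero, which could make an unaffordable or refused drug look cheap. Report the number of unfilled or denied prescriptions by arm beside the cost result. The total can also include only what the pharmacy records hold, and the report should say so.
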